
## STUDY PROTOCOL

	
A point estimate and its 95% confidence interval (CI) will be derived for the slope <math>\beta</math> to evaluate dose proportionality. The goodness of fit of the linear model will also be investigated. To evaluate dose proportionality graphically, plots of AUC and <math>C_{max}</math> versus dose, AUC and <math>C_{max}</math> (expressed on the log scale) versus dose (expressed on the log scale), and dose normalised AUC and <math>C_{max}</math> versus dose will be produced for each individual subject and means. Details will be specified in a Statistical Analysis Plan.
 
(v) Food effect (Part 2) A linear mixed model will be used to analyse log-transformed <math>AUC_{0-\infty}</math>, <math>AUC_{0-last}</math> and <math>C_{max}</math>, with fed state (fed, fasted) as fixed effects and subject as a random effect. Difference in least square (LS) means and corresponding 90% CI will be back-transformed to obtain the estimate and CI of geometric mean ratio of fed to fasted. The reference treatment will be the corresponding dose from Part 1.
 
(vi) Dose proportionality (Part 3) Dose proportionality will be assessed by <math>AUC_{0-24}</math> and <math>C_{max}</math> on Day 1 and <math>AUC_{0-t}</math> and <math>C_{max}</math> on the last day of dosing using the power model. A linear model will be used to fit the power model after log-transformation of the parameter of interest. The model will include the log-transformed dose as fixed effect. A point estimate and its 95% CI will be derived for the slope <math>\beta</math>.
 
(vii) Assessment of steady state (Part 3) The ratio of trough concentration on each day (Day 2 to Day 13) compared to trough concentration on last dosing day (anticipated as Day 14 but could be as late as Day 28) will be summarised using descriptive statistics. Mean trough concentrations versus day will also be presented with all dose levels overlaid on the same plot.
 
(viii) Assessment of linearity and accumulation (Part 3) The linearity factor (<math>LF = AUC_{0-t}[\text{last day of dosing}] / AUC_{0-\infty}[\text{Day 1}]</math>) and the ratio of accumulation (<math>RA = AUC_{0-t}[\text{last day of dosing}] / AUC_{0-\infty}[\text{Day 1}]</math>) will be summarised using descriptive statistics. The LF will not be calculated if <math>AUC_{0-\infty}</math> on Day 1 cannot be calculated precisely.
 
(ix) Gender effect (Part 4) A linear model will be used to analyse log-transformed <math>AUC_{0-\infty}</math>, <math>AUC_{0-last}</math> and <math>C_{max}</math>, with gender (male, female) as fixed effects. Difference in LS means and corresponding 90% CI will be back-transformed to obtain the estimate and CI of geometric mean ratio comparing female to male. The reference treatment will be the corresponding dose from Part 1.
 
(x) Race effect (Part 5) A linear model will be used to analyse log-transformed <math>AUC_{0-\infty}</math>, <math>AUC_{0-last}</math> and <math>C_{max}</math>, with race (Caucasian, Japanese) as fixed effects. Difference in LS means and corresponding 90% CI will be back-transformed to obtain the estimate and CI of geometric mean ratio comparing Japanese to Caucasian. The reference treatment will be the corresponding dose from Part 1.

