**3.3 Rationale for dose selection**

[REDACTED]

[REDACTED]

[REDACTED]

Dose escalation up to [REDACTED] in Part 1 will only proceed following careful clinical monitoring showing acceptable safety and tolerability. In addition, dose escalation will not continue if the mean exposure limit of 45,250 ng.h/mL (AUC0-24h) in a single subject is expected to be exceeded.

Dose escalation is planned in Part 1. The dose escalation factor applied after each cohort will not exceed five-fold for Cohorts 1 to 2, four-fold for Cohorts 2 to 3 and will not exceed three-fold thereafter. The starting dose for Cohort 1 will be [REDACTED]. The anticipated dosing schedule is [REDACTED], [REDACTED] and [REDACTED]. A report will be prepared for each cohort in Part 1 containing safety and tolerability data (up to at least 48 hours post-dose) and PK data (up to at least 24 hours post-dose) from a minimum of 6 subjects (MT-6345 n≥4) in the preceding cohort. The Principal Investigator and Sponsor will review the data and agree whether to progress to the next dose level and dose selection.

Europe/Mitsubishi Tanabe Pharma Europe Ltd  
STUDY PROTOCOL

If it is not appropriate to escalate the dose for the next planned cohort, an intermediate dose may be selected; alternatively no further dose escalation will take place (see Sections 3.4 and 4.6).

In Part 2, the effect of food on MT-6345 will be investigated. The anticipated dose level is [REDACTED] however, the dose will not be confirmed until safety, tolerability and PK data from the intended dose level in Part 1 has been reviewed and deemed acceptable.

In Part 3, the anticipated starting dose will be [REDACTED]. Progression to the next dose level and dose selection will be based on available safety, tolerability and PK data from Part 1 and the preceding cohort in Part 3 (safety and tolerability data up to 72 hours after the last dose and available PK data up to 24 hours after the last dose, from a minimum of 10 subjects [MT-6345 n≥7] in the preceding dose cohort). The anticipated doses are [REDACTED] and [REDACTED]

In Parts 4 and 5 the dose level is anticipated to be [REDACTED] however the dose selected will not be confirmed nor administered until safety, tolerability and PK data from the intended dose level in Part 1 has been reviewed and deemed acceptable.

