**10.3 Statistical analysis****10.3.1 General considerations**

The SAP, containing detailed data handling, analysis methods, outputs (tables, figures and listings), will be developed and approved prior to database lock. Additional analysis may be performed if deemed necessary. Any deviations from the planned analysis will be described and justified in a separate document and in the Clinical Study Report (CSR).

All subjects who received placebo for Part 1 will be pooled into a single placebo group (dose level 0) and all subjects who received placebo for Part 3 will be pooled into a single placebo group (dose level 0) for the final statistical analysis. The assignment of subjects to the various analysis sets will be listed and summarised. Summaries for Parts 2, 4 and 5 will be done by treatment group and by status, with corresponding dose cohort from Part 1.

STUDY PROTOCOL

---

All variables will be summarised by treatment group/cohort. Unless otherwise stated, continuous data will be summarised descriptively using N (number of subjects), n (number of observations), mean, standard deviation (SD), minimum, median and maximum. Categorical data will be summarised using frequency tables (frequency and percentage). The term "log-transformation" refers to the natural logarithmic transformation throughout the SAP.

All individual subject data will be listed.

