##### **10.3.5.4 Dose proportionality (Part 1)**

The PK parameters (AUC0-∞, AUC0-last and Cmax) from the SAD part will be used in the exploration of dose proportionality. The overall dose proportionality will first be evaluated using the power model. A linear model will be used to fit the power model, after log-transformation of the parameter of interest (e.g., AUC [AUC0-∞, AUC0-last] or Cmax). The model will include the log-transformed dose as fixed effect. A schematic representation of the proposed model is included below:

$$\text{Log (AUC or C}_{\text{max}}\text{)} = \alpha + \beta \cdot \text{log (Dose)} + \varepsilon$$

Where  $\alpha$  and  $\beta$  are the regression coefficients and  $\varepsilon$  is the error term.

A point estimate and its 95% confidence interval (CI) will be derived for the slope  $\beta$  to evaluate dose proportionality. The goodness of fit of the linear model will also be investigated.

To evaluate dose proportionality graphically, the following plots will be produced for each individual subject and means:

- AUC and  $C_{max}$  versus dose.
- AUC and  $C_{max}$  (expressed on the log scale) versus dose (expressed on the log scale).
- Dose normalised AUC and  $C_{max}$  versus dose.

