## 1. INTRODUCTION

This statistical analysis plan (SAP) is based on the final protocol (v2.0) dated 12-DEC-2018. The plan covers statistical analysis, tabulations and listings of the study data to investigate the safety, tolerability and pharmacokinetics of single and multiple ascending doses of MT-6345 compared to placebo in healthy subjects.

Any statistical analysis details described in this document supersede any description of statistical analysis in the protocol.

This study was terminated due to brain changes in male rats in the 13-week tox study. Subjects were enrolled in only Part 1, Part 2 and Part 3. Some assessments which were not performed are grayed out in this SAP.

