#### **3.3.2. Actual Sample Size**

This study was terminated due to brain changes in male rats in the 13-week tox study. Subjects were enrolled in only Part 1, Part 2 and Part 3. 52 subjects were actually randomized as follows.

Part 1: 44 subjects in total; 8 subjects for [REDACTED] and [REDACTED] cohorts respectively, and 6 subjects for [REDACTED] and [REDACTED] cohorts, respectively.

Part 2: 6 subjects returned to received the same [REDACTED] dose as in Part 1 (active or placebo), are therefore not unique patients and are not counted again in the total number of exposed subjects.

Part 3: 8 subjects in the [REDACTED] cohort

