### 8.3.3. Dose Proportionality

Dose proportionality will be assessed by  $AUC_{0-\text{last}}$ ,  $AUC_{0-\infty}$  and  $C_{\max}$  for single dose using a power model. A schematic representation of this is outlined below:

$$AUC_{0-\text{last}} \text{ or } AUC_{0-\infty} \text{ or } C_{\max} = e^{\mu} \cdot Dose^{\beta} \cdot e^{\varepsilon}$$

The following linear model will be fitted to the log-transformed parameters of interest:

$$\log_e (AUC_{0-\text{last}} \text{ or } AUC_{0-\infty} \text{ or } C_{\max}) = \mu + \beta \cdot \log_e (Dose) + \varepsilon$$

Where  $\mu$  and  $\beta$  are the regression intercept and slope coefficients and  $\varepsilon$  is the error term; assumed to be normally distributed.

The estimate obtained for  $\beta$  is a measure of dose proportionality. Dose proportionality will be

concluded if the 95% CI for  $\beta$  includes the value 1. The parameter estimates and the 95% CIs will be produced.

The evaluation of the model fit will be done by lack-of-fit. In the case where dose-proportionality across all investigated dose groups cannot be established, additional exploratory analysis will be done by either fitting power model on subgroup of investigated dose groups or other data-driven analysis, if deemed appropriate.

To evaluate dose proportionality graphically the following plots will be produced:

- Individual plots of  $AUC_{0\text{-last}}$ ,  $AUC_{0\text{-}\infty}$  and  $C_{\max}$  versus dose levels on linear and log scales (with the fitted linear regression line for log scales)
- Individual plots for  $AUC_{0\text{-last}}/\text{dose}$ ,  $AUC_{0\text{-}\infty}/\text{dose}$  and  $C_{\max}/\text{dose}$  by dose level

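### SAP 8.3.3 declares dose proportionality whenever the 95% CI for the slope contains 1, so a failure to detect a departure is reported as proportionality

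*SAP*

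**What the plan says.** SAP 8.3.3 regresses the natural log of AUC0-last, AUC0-∞ and Cmax on log dose for the single-dose data. It takes the slope β as the measure of proportionality and states that proportionality will be "concluded if the 95% CI for $\beta$ includes the value 1". Estimates, 95% CIs, a lack-of-fit evaluation and plots are also planned, but the verdict is not made conditional on any of them. A further step begins "In the case where dose-proportionality across all investigated dose groups cannot be established" and allows the model to be refitted on a subset of dose groups, or another data-driven analysis, where judged appropriate.

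Protocol 10.3.5.4 has no such rule. It says "A point estimate and its 95% confidence interval (CI) will be derived for the slope", adds goodness of fit and plots, and stops there. Item (iv) of the Protocol Synopsis leaves the rest to the SAP: "Details will be specified in a Statistical Analysis Plan". SAP section 1 then gives the SAP precedence: "Any statistical analysis details described in this document supersede any description of statistical analysis in the protocol". The rule is thus an addition that governs the analysis. It does not contradict the protocol.

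**The concern.** A 95% CI that contains 1 is the same event as failing to reject β = 1 at two-sided 5%. It shows that the data did not detect a departure. It does not show that exposure rises in proportion to dose. The rule has no limit on β and no cap on interval width, so a wide interval earns the same verdict as a narrow one centred on 1.

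The incentive also runs the wrong way. If the true slope is not 1, more variability or fewer subjects raises the chance of being called proportional. Nothing in the design guards against this, because both documents say that the sample size has no formal statistical basis.

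At stake is the stated conclusion on single-dose proportionality, which could come from imprecision alone.

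**Working it through.** The plan gives no power, margin or precision figure for this analysis, so there is nothing of its own to reproduce. The check asks how often the rule returns a proportional verdict when exposure is not proportional.

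**Inputs from the documents**
- Rule: the two-sided 95% CI for β contains 1 (SAP 8.3.3).
- Planned Part 1: six cohorts with 6 active subjects each, so 36 active.
- Actual Part 1: "Part 1: 44 subjects in total" (SAP 3.3.2), in cohorts of 8 and of 6. Four of 8 plus two of 6 gives 32 + 12 = 44.
- Escalation steps "will not exceed five-fold for Cohorts 1 to 2, four-fold for Cohorts 2 to 3 and will not exceed three-fold thereafter" (Protocol 3.3), so the range is at most 5 × 4 × 3 × 3 × 3 = 540-fold.

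**Assumptions** (redacted or not stated)
- Active subjects: 36, or 32 if each smaller cohort had 2 on placebo (4 × 6 + 2 × 4). For 32, all 15 placements of the two smaller cohorts were tried.
- Doses: 1, 2, 4, 8, 16, 32; six log-evenly spaced doses over 100-fold; and 1, 5, 20, 60, 180, 540.
- CV: 20, 30, 50 and 70%.

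**Formulas**
- σ = √ln(1 + CV²); SE(β) = σ/√Sxx, where Sxx is the sum of squares of log dose; n − 2 degrees of freedom.
- A fold-departure F in dose-normalised exposure over a dose range r corresponds to β = 1 + ln F / ln r.
- P(verdict is proportional) = P(|b − 1| ≤ t·SE), where b is the estimated slope and t the 97.5% point, from the noncentral t with noncentrality (β − 1)/SE.

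**One case in full** (36 active, 32-fold range, CV 50%, true 2-fold departure)
- σ = √ln 1.25 = 0.472; Sxx = 6 × 17.5 × (ln 2)² = 50.4; SE = 0.472/√50.4 = 0.0665.
- β = 1 + ln 2/ln 32 = 1.20; noncentrality = 0.20/0.0665 = 3.0; t with 34 df = 2.03.
- P = 17%.
- The CI half-width over the range is exp(2.03 × 0.0665 × ln 32) = 1.6. An estimated departure of up to about 1.6-fold would still be labelled proportional.

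**Chance that a true departure is called proportional** (span over the three dose ranges and, for 32 active, the 15 placements)

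| True departure | Active | CV 20% | CV 30% | CV 50% | CV 70% |
|---|---|---|---|---|---|
| 1.5-fold | 36 | 2% | 21–23% | 60–61% | 75–76% |
| 1.5-fold | 32 | 2–6% | 22–35% | 60–69% | 75–81% |
| 2-fold | 36 | 0% | 0.3–0.4% | 17–18% | 41–42% |
| 2-fold | 32 | 0% | 0.4–2% | 17–30% | 42–54% |
| 3-fold | 36 | 0% | 0% | 0.4–0.5% | 7% |
| 3-fold | 32 | 0% | 0% | 0.4–2.3% | 7–16% |

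Some 3-fold cells at CV 20% do not evaluate numerically. They cannot exceed the 2-fold value above them, which is 0%.

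**Largest estimated departure still labelled proportional**, at CV 20/30/50/70%: 1.2/1.3/1.6/1.9-fold with 36 active, and up to 1.3/1.4/1.7/2.1-fold with 32.

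**Effect of sample size** (2-fold departure, CV 50%, 32-fold range): 4, 6 or 12 active per cohort gives 35%, 17% and 1.3%. The smallest study is the most likely to be called proportional.

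**Subset refit.** The SAP does not say what rule applies after a refit. If it is the same one, three cohorts of 6 active over a 9-fold range with true β = 0.80 (9^−0.20 = 0.64, so dose-normalised exposure 36% lower at the top dose) are called proportional about 32, 67 and 80% of the time at CV 30, 50 and 70%.

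**The case against.** The case for leaving the sentence alone concerns weight, not logic.

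- **Low consequence.** The protocol calls this an exploration of proportionality. It is a secondary PK analysis in a terminated study, no document ties a dose or go/no-go decision to the verdict, and the rule covers single doses only. The estimate, its CI, lack-of-fit and plots are all produced, so a reader would see a wide interval beside the verdict. Further work is not barred either: Protocol 10.3.1 says "Additional analysis may be performed if deemed necessary". All of this stands and limits the severity.
- **The size depends on values that the documents do not give.** At a CV of 30% or less the rule rarely misses a 2-fold departure. The large 2-fold figures need a CV of about 50% or more, and nothing in either document indicates that. This stands.
- **The 32-active upper ends are worst cases.** If the smaller cohorts had 5 active each (34 in all), the 2-fold maxima fall from 30% to 23% at CV 50% and from 54% to 48% at CV 70%. This trims the upper ends and leaves the direction unchanged.
- **Lack of fit might also count as proportionality not being established.** The text allows that reading. It does not help when the line fits well and the interval is merely wide.

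None of these points makes the sentence correct. It still instructs the author to state a conclusion that the interval may not support.

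**Conclusion.** The concern holds. The rule treats non-rejection of β = 1 as evidence of proportionality, and nothing in the SAP or protocol restrains it. That follows from the text alone and does not depend on any assumed value.

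The practical size does depend on assumptions. If the CV is 30% or less, a 2-fold departure over the range is rarely missed, but a 1.5-fold departure is called proportional in up to about a third of studies at CV 30% (21–35%). At CV 50–70%, a 2-fold departure is called proportional 17–54% of the time. The sentence should be fixed. The effect is confined to one reported conclusion of a secondary analysis whose supporting estimates will be visible.

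**What to change.** Delete the sentence in SAP 8.3.3 that sets the verdict. Replace it with text to this effect:

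> The estimate of β and its 95% CI will be reported together with the implied fold-departure from proportionality over the studied doses, r^(β−1), and its CI, where r is the ratio of highest to lowest dose. A CI containing 1 will be interpreted only as no departure having been detected.

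The refit clause needs a matching edit, because its trigger would otherwise lose its definition. Exploratory refits should be considered if the CI excludes 1, or if lack-of-fit or the plots suggest a departure.

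This returns to the estimate-and-interval approach of Protocol 10.3.5.4. The r^(β−1) output goes slightly beyond what the logical fault requires, but it puts the result on a scale that can be judged. Limits for a pass/fail verdict, fixed in advance, are optional and for the sponsor to choose; the fix does not need them.

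The cost is one sentence, the trigger wording and one derived quantity with its CI. No new data or model is needed. The plan loses its automatic verdict, which the current rule gives 95% of the time when β is exactly 1, and imprecise data will have to be reported as inconclusive. At CV 70%, for example, departures of up to about 1.9-fold (36 active) or 2.1-fold (32 active) would not be excluded even with an estimated slope of exactly 1.

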### 8.3.4. Steady State

Trough concentrations are the pre-dose concentrations each day (Day 1 to Day X when data is available). The trough concentrations will be listed.

Following plots will be produced:

- Individual trough concentration vs. actual time on linear/linear scale
- Mean trough concentration (+SD) vs. nominal time on linear/linear .

1000 JOURNAL OF CLIMATE

#### 8.4.1. [REDACTED]

11. **What is the primary purpose of the study?** (check all that apply)

#### 8.4.2. [REDACTED]

For more information, contact the Office of the Vice President for Research and Economic Development at [contact] or [[contact]](mailto:[contact]).

#### 8.4.3. [REDACTED]

\_\_\_\_\_

#### 8.4.4. [REDACTED]

For more information, contact the Office of the Vice President for Research and Economic Development at [contact] or [[contact]](mailto:[contact]).

## 9 DATA PRESENTATION CONVENTIONS

### 9.1 Number of Digits to Report

#### (1) Non-PK related

Statistic	Specification	Apply to
Minimum, Maximum	Same number of DPs as the data provided in the datasets	All original (i.e. non-derived)
	see section 7.3	All derived data
Mean, Median, SD, SE, Confidence intervals	One more DP than above	All
Percentages *1	1 DP	All
Ratios	3 DPs	All

\*1 Percentages: use 1 DP, except for the following cases:

If the percentage is equal to 0, then leave blank, do not use (0)

If the percentage is equal to 100, then use "(100)" without a decimal

#### (2) PK Plasma Concentration

Statistic	Specification
Individual value, Minimum, Maximum, Mean, SD, Median	4 significant digits

#### (3) PK Parameters

Statistic	Specification
Individual value, Mean, SD, Minimum, Maximum, Median, Geometric mean	$C_{\max}$ : the same significant digits as they are reported $t_{\max}^*$ : 2 DPs $t_{1/2}$ : 2DPs Kel: 4DPs Other parameters: 3 significant digits
CV%, Geometric CV%	1 DP

\*:  $t_{\max}$  will be expressed basically in terms of median and range

### 9.2 Treatments to Report

For Parts 1 (single dose ascending part of study), summaries will be done by dose level with all placebo subjects from each cohort pooled and presented side-by-side with active dose levels. All subjects who received placebo for Part 3 will be pooled into a single placebo group (dose level 0) for the final statistical analysis.

All tables will be sorted by (ascending) dose level, and all active doses will be shown after placebo.

Part 1:

Placebo (N=XX)	MT - 6345 [REDACTED] (N=XX)					
-------------------	-----------------------------------	-----------------------------------	-----------------------------------	-----------------------------------	-----------------------------------	-----------------------------------

Part 2(For Table):

Fed	Fasted
Placebo (N=XX) [REDACTED] (N=XX)	MT - 6345 [REDACTED] Placebo (N=XX) [REDACTED] (N=XX)

Part 2(For Listing):

Placebo - Fed/Fasted	MT-6345 [REDACTED] -
----------------------	----------------------------

Part 3:

Placebo (N=XX)	MT - 6345 [REDACTED] (N=XX)
-------------------	-----------------------------------

### 9.3 Analysis Visits to Report

(1) Non-PK related

For Part 1 and 2

Analysis Visit	Apply to			
	Laboratory Tests	Vital Signs	12-Lead ECG (standard safety)	Physical Examinations
Screening	X	X	X	X
Day -1	X	X	X	
Day 1 / Pre dose		X	X	
Day 1 / 1h		X	X	
Day 1 / 2h		X	X	
Day 1 / 3h			X	
Day 1 / 4h		X		
Day 1 / 8h		X	X	
Day 1 / 12h		X		
Day 2	X	X	X	
Day 3	X	X		
Day 15(FU)	X	X	X	X

For Part 3

Analysis Visit	Apply to			
	Laboratory Tests	Vital Signs	12-Lead ECG (standard safety)	Physical Examinations
Screening	X	X	X	X
Day -1 / Baseline	X	X	X	
Day 1 / Baseline		X	X	
Day 2	X	X	X	
Day 3	X	X	X	
Day 15(FU)	X	X	X	X

Unscheduled visits and retests (same visit number assigned) will not be displayed in by-visit summary tables, but will be included in the data listings.

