**Day 1 (post-dose)**

- Vital signs (including supine blood pressure, pulse rate, respiratory rate and oral body temperature) at 1, 2, 4, 8 and 12 hours post-dose.
- 12-lead ECG at 1, 2, 3 and 8 hours post-dose.
- PK blood sampling for MT-6345 at 0.5, 1, 1.5, 2, 3, 4, 5, 6, 8, 12 and 16 hours post-dose.
- [REDACTED]
- PK urine sampling for MT-6345 at 0 hours to 24 hours post-dose.
- [REDACTED]
- [REDACTED]
- AE and concomitant medication recording.

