**10.3.4.2 Vital signs and electrocardiograms**

Vital signs and 12-lead ECG variables and changes from baseline will be summarised (N, n, mean, SD, median, minimum and maximum) at each time point for each study Part by dose level and by fed state, gender and race category, where appropriate.

The baseline for the vital sign parameters and 12-lead ECG measurements will be the last valid assessment obtained on Day 1 prior to the administration of double-blind IMP.

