Concomitant medication															

Abbreviations: ADM=admission; BMI=body mass index; ECG=electrocardiogram; IMP=Investigational Medicinal Product; LDD=last day of dosing; MDD=midpoint dosing day;

PK=pharmacokinetic; QTcF=corrected QT interval using Fridericia's formula.

1. e.g. if duration of dosing is 14 days then should be on Day 7 (+/- 2 days)
2. Subjects will receive a once daily dose of MT-6345 for at least 14 days. Dosing can be extended out as far as Day 28, so the day before the LDD can be Day 13 up to a maximum of Day 27.
3. The LDD will be Day 14, at a minimum. Dosing can be extended out as far as Day 28.
4. Subjects admitted on the evening of Day -2; assessments will be performed on Day -1. Subjects will be discharged 72 hours after the LDD (Day 17 at minimum, Day 31 at maximum).
5. Conducted by a Consultant Ophthalmologist. Further details can be found in Section 6.5.1
6. Urine drugs of abuse screen will include tests for methadone, cocaine, tetrahydrocannabinol, benzodiazepines, barbiturates, amphetamines and opiates. Carbon monoxide and alcohol breath tests will also be performed.
7. Vital sign assessments to be conducted at pre-dose on Day 2 to the LDD.
8. Continuous ECG will be collected from approximately 24 hours prior to dosing on Day -1 until pre-dosing on Day1; and from pre-dose on the LDD to 24 hours after last dosing (LDD +1). ECG extractions to occur at each PK blood sampling time point during this period.
9. A 12-lead ECG (heart rate and cardiac intervals: PR, QRS, QT and QTcF) will be performed at Day -1 (-0.5, 1, 2, 3 and 8 hours relative to expected dose time on Day 1); Days 1, 8 and LDD (at pre-dose, 1, 2, 3 and 8 hours post-dose); Days 2 to 7 (pre-dose); Days 9 to the day before the LDD (pre-dose); and 24 hours and 72 hours after the LDD (LDD +1 and LDD +3).
10. If dosing is extended beyond 14 days, a blood sample will be taken on Day 14 and every 7 days thereafter.
11. PK blood samples for MT-6345 will be collected on Day 1 (pre-dose and at 0.5, 1, 1.5, 2, 3, 4, 5, 6, 8, 12 and 16 hours post-dose), Day 2 to LDD -1 (pre-dose), LDD (pre-dose and at 0.5, 1, 1.5, 2, 3, 4, 5, 6, 8, 12 and 16 hours post-dose), and on LDD +1 (24 hours post last dose), LDD +2 (48 hours post last dose) and LDD +3 (72 hours post last dose).

13. PK urine samples for MT-6345 will be collected at Day-1 (-24 hours 0 hours), Day1 (0 hours to 24 hours) and LDD(0 hours to 24 hours).

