### 8.2.3 Vital Signs

Absolute values will be summarized and presented at each timepoint for each study part by dose level and by fed state for the following parameters.

- Systolic Blood Pressure (mmHg)
- Diastolic Blood Pressure (mmHg)
- Heart Rate (bpm)
- Respiratory Rate (breath/min)
- Oral Body Temperature (°C)
- Overall evaluation

All data will be listed.

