## **8.3 Pharmacokinetics Evaluation**

### **8.3.1. Plasma and Urine Concentration**

Plasma MT-6345 concentrations will be summarized at each nominal sampling point by dose group for single dose group, multiple dose group and food state. All plasma and urine concentrations will also be listed.

Plots for single dose group;

For each dose group and food state, individual plasma concentrations vs. actual time for 0-24hr and 0-t hr (t: last sampling time point) will be plotted on both linear/linear and log/linear scales for MT-6345. Mean plasma concentrations vs. nominal time curves for 0-24hr and 0-t hr will be plotted on both linear/linear (+SD) and log/linear scales overlaid by all dose groups MT-6345. Plots will also be prepared overlaid by food state, as appropriate.

Plots for multiple dose group;

For each dose group, individual plasma concentrations vs. actual time will be plotted on both linear/linear and log/linear scales for MT-6345. Mean plasma concentration vs. nominal time curves will be plotted on both linear/linear (+SD) and log/linear scales overlaid by all dose groups for MT-6345. Plots will also be prepared overlaid, as appropriate.

The following mean plots for MT-6345 will be produced:

- Day all: plots on linear/linear (+SD) scale and log/linear scales
- Day 1: plots on linear/linear (+SD) scale for 0-24 hr

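### The Part 3 table in SAP 9.3 has no Day 1 post-dose rows for vital signs or ECG, which contradicts SAP 8.2.3 and 8.2.4; the omission is not declared

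*SAP*

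**What the plan says.** In SAP 9.3, the table for Parts 1 and 2 gives Day 1 rows at pre-dose and at 1, 2, 3, 4, 8 and 12 h. The Part 3 table below it has six rows: Screening, "Day -1 / Baseline", a Day 1 row also labelled as baseline, Day 2, Day 3 and Day 15 follow-up.

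For the Part 3 Day 1 post-dose period, protocol 5.2.2.2 schedules vital signs ("respiratory rate and oral body temperature) at 1, 2, 4, 8 and 12 hours post-dose") and ECGs ("12-lead ECG at 1, 2, 3 and 8 hours post-dose"). The SAP repeats the ECG times in footnote 9 to its own Part 3 confinement schedule (SAP Table 3): "Days 1, 8 and LDD (at pre-dose, 1, 2, 3 and 8 hours post-dose".

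On tabulation, SAP 8.2.3 states for vital signs: "Absolute values will be summarized and presented at each timepoint for each study part". SAP 8.2.4 sets the same rule for ECGs. Protocol 10.3.4.2 likewise plans these summaries "at each time point for each study Part by dose level".

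SAP Section 10 names the planned analyses that were not done, including the change-from-baseline summaries. It does not mention dropping Part 3 time points. SAP Sections 1 and 3.1.2 report that the study was terminated early and that assessments not performed are shaded grey.

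**The concern.** Vital signs and ECG parameters are primary endpoints. With the change-from-baseline summaries dropped, the tables of absolute values by time point are the main remaining summary of how these measurements move after dosing. A programmer who builds the Part 3 tables from 9.3 would go from the pre-dose Day 1 value straight to Day 2. A group-level shift during the first day that had faded by the next morning would not show in those tables. A programmer who works from 8.2.3 and 8.2.4 would include the within-day times. Two faithful readings of one SAP therefore give different primary safety tables.

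The protocol cannot settle this, because SAP Section 1 says that its analysis details supersede those in the protocol. The conflict has to be resolved inside the SAP.

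**Working it through.** The plan gives no figure of its own to reproduce. The check sets the schedule against the rows to be reported.

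**Inputs.** Scheduled times are from protocol 5.2.2.1 (Parts 1 and 2) and 5.2.2.2 (Part 3). Rows are from SAP 9.3. The number randomised to Part 3, 8, is from SAP 3.3.2.

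| Day 1 post-dose | Scheduled times | Rows in 9.3, Parts 1 and 2 | Rows in 9.3, Part 3 |
|---|---|---|---|
| Vital signs | 1, 2, 4, 8, 12 h (5) | 5 of 5 | 0 of 5 |
| ECG | 1, 2, 3, 8 h (4) | 4 of 4 | 0 of 4 |

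**Scheduled assessments without a row.** Subjects × times:
- vital signs: 8 × 5 = 40
- ECG: 8 × 4 = 32
- together: 40 + 32 = 72

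These are upper limits taken from the schedule. They are not counts of data held.

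**First tabulated post-dose value.** The row after Day 1 is Day 2. Protocol 5.2.2.2 places the Day 2 vital signs and ECG before that day's dose, so about 24 h after the first dose.

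**How long dosing may have lasted.** Protocol 5.2.4.2 sets Part 3 follow-up at 14 ± 1 days after the last dose, so follow-up day = last dosing day + 14 ± 1:
- last dose on Day 1: Days 14 to 16
- last dose on Day 2: Days 15 to 17
- last dose on Day 14: Days 27 to 29

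A Day 15 follow-up row fits a last dose on Day 1 or 2, not Day 14. If that row reflects what happened, the Day 1 readings could be most of the within-day safety data in Part 3. The row may instead have been carried over from the table for Parts 1 and 2, so this is only suggestive.

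**Does early termination explain the gap?** It could explain why no rows stand between Day 3 and follow-up. It explains Day 1 less readily: 9.3 keeps Days 2 and 3, and SAP 8.3.1 still plans for the multiple-dose group "Day 1: plots on linear/linear (+SD) scale for 0-24 hr".

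**The case against.** The strongest reply is that the SAP does plan these summaries. Sections 8.2.3 and 8.2.4 belong to the methodology chapter, 9.3 belongs to the presentation conventions, and nothing says that 9.3 prevails. This stands. A reader might infer that the SAP has decided to drop the within-day tables, but the text supports only a contradiction. It still needs correcting, because 9.3 is the list that names the rows and its closing note concerns what appears in by-visit tables.

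A second reply is that the assessments may never have been done. The grey shading cannot be seen in the text available here, and the vital-sign and ECG rows of SAP Table 3 did not survive extraction. This also stands, so 40 and 32 must not be read as data collected and left out. The planned Day 1 concentration plot is weak evidence the other way: SAP 7.2 also keeps sampling windows around the last dosing day, and Appendix 1 keeps Day 14 ratios, so some pharmacokinetic text may simply be left over from the original plan.

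Third, a reader might infer that the tables miss peak exposure, or that an effect would be visible only in listings. Neither document gives a tmax, so the peak is an inference; what can be said is that no scheduled time between dosing and about 24 h has a row. Other outputs remain. Clinically significant vital-sign and ECG abnormalities are reported as adverse events (protocol 6.5.2 and 6.5.3) and tabulated, and the QTcF limit counts in SAP 8.2.4 are not tied to the rows of 9.3. With 8 subjects and no inferential safety analysis planned, the listings can be read in full.

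Last, neither document plans a comparison of Part 1 with Part 3 at matching times, so the loss of one is not a departure from the plan.

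**Conclusion.** The point holds as an undeclared inconsistency within the SAP that bears on the by-time tables of two primary safety endpoints. If 9.3 governs, the Part 3 tables cover 0 of 5 scheduled vital-sign times and 0 of 4 scheduled ECG times after the Day 1 dose. That is up to 40 and 32 assessments in 8 subjects, on the assumption that all were performed as scheduled. The consequence is limited to those summary tables.

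The repeated baseline label in the Part 3 table is a matter of tidiness. SAP 7.2 already defines baseline as the last value before first intake, and the change-from-baseline summaries are not produced, so the label has no analytic effect.

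**What to change.** In the Part 3 table of SAP 9.3, add Day 1 rows at 1, 2, 4, 8 and 12 h for vital signs and at 1, 2, 3 and 8 h for ECG, as in the table for Parts 1 and 2. If early termination meant that these assessments were not performed, say so in Section 10 instead. While the table is open, leave one baseline label per parameter: Day -1 for laboratory tests, and Day 1 pre-dose for vital signs and ECG, as in protocol 10.3.4.2 and 10.3.4.3.

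The cost is a few extra rows in tables already planned, or one sentence in Section 10. No new data collection or method is needed.
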